6.3.5 Decimal Places

For summary statistics, n will be reported as a whole number. Means, medians and percentiles will be displayed to one more decimal place than the data, dispersion statistics (e.g., standard deviation) will have two more decimal places, and the minimum and maximum will be displayed to the same number of decimal places as reported in the raw data. Percentages will be displayed with one decimal place. All data presented in the individual participant listings will be as recorded on the eCRF.

6.3.6 Data Displays

All clinical data tabulations, figures and listings will be generated as individual Rich Text Format (.rtf) files using [REDACTED]¹. Data summaries and graphical analyses will be reported within Section 14 of the CSR and individual participant data listings within Appendix 16.2 of the CSR.

Participant disposition, baseline characteristics, demographic, compliance, concomitant medication, and adverse event data will be presented by treatment group and overall. Other safety data will be presented by treatment group only.

Please note: Data from study Part A will be listed only.

Treatment group labels will be displayed as follows:

PLN-74809	PLN-74809	PLN-74809	PLN-74809	All	
(40 mg)	(80 mg)	(160 mg)	(320 mg)	PLN-74809	Placebo
(N=XX)	(N=XX)	(N=XX)	(N=XX)	(N=XX)	(N=XX)

QMD [REDACTED]	[REDACTED]
Confidentiality Statement	
This document is the property of [REDACTED] and may not be duplicated, copied, altered or removed from company without prior approval from [REDACTED] or in compliance with [REDACTED].	

[REDACTED]

Controlled Quality Management Document		
	Sponsor:	Pliant Therapeutics Inc.
	Protocol Number:	PLN-74809-IPF-202
STATISTICAL ANALYSIS PLAN. PHASE 2-3-4		

Listings will be sorted in the following order, study part (Parts B/C/D/A), treatment group, participant number, parameter, and visit unless otherwise stated. All data will be listed, participants who were not randomized will be displayed after the randomized treatment groups.

6.4 Participant Disposition

Participant disposition will be summarized by treatment group and overall, for the Safety Population as follows:

- The number of participants entering the study.
- The number of participants in each analysis population.
- The number of participants completing study treatment.
- The number of participants not completing study treatment and reason for non-completion of study treatment.
- The number of participants completing the study.
- The number of participants with early termination and the reasons for early termination.
- The reasons for exclusion from the Efficacy Per-Protocol Population will be listed.

6.5 Protocol Deviations

All reported protocol deviations (PD) will be summarized by treatment group, PD category and PD classification (Major, Minor, and total) as well as listed.

6.6 Baseline Comparability

Comparability of treatment groups with respect to participant demographics and baseline characteristics will be assessed in a descriptive manner, but no formal statistical testing will be performed.

Baseline summaries will be presented by treatment group and overall, for the following variables based on the Safety Population:

Demographic Data

- Age at Informed Consent (years)
- Sex
- Ethnicity

Confidentiality Statement	
This document is the property of [REDACTED] and may not be duplicated, copied, altered or removed from company without prior approval from [REDACTED] or in compliance with [REDACTED].	

[REDACTED]

Controlled Quality Management Document		
	Sponsor:	Pliant Therapeutics Inc.
	Protocol Number:	PLN-74809-IPF-202
STATISTICAL ANALYSIS PLAN. PHASE 2-3-4		

- Race, where more than one race is selected the participant will be presented under the ‘Multiple races’ category in the summary but each selected race will be identified in the listing.

Baseline Characteristics

- Weight at Screening (kg)
- Height at Screening (cm)
- BMI at Screening (kg/m²)
- Fertility Status (Childbearing Potential, Postmenopausal, Surgically Sterile)
- Participant taking nintedanib or pirfenidone at Screening

Clinical Characteristics

- Pulmonary Function at Screening
- Pulmonary Function at Baseline
- DLCO Lung Function Assessment at Screening (if repeated, the last non-missing value before first dose will be taken)
- GAP Index Score and Staging
- Duration Since Diagnosis at Screening (first date reported for Idiopathic Pulmonary Fibrosis, Pulmonary Fibrosis or Interstitial Lung Disease)
- Duration of Standard of Care at Randomization (defined as the number of months from start date of nintedanib or pirfenidone to date of randomization)

Additional summaries will be completed for Part D only participants as well as placebo participants by study part.

6.7 Medical History

Separate tabulations of prior and ongoing conditions at screening will be presented by treatment group and overall, for the Safety Population. All reported medical history data will be listed. Non-pharmacological procedures will be provided as a separate listing.

QM [REDACTED]	[REDACTED]
Confidentiality Statement	
This document is the property of [REDACTED] and may not be duplicated, copied, altered or removed from company without prior approval from [REDACTED] or in compliance with [REDACTED].	

[REDACTED]

Controlled Quality Management Document	
	Sponsor: Pliant Therapeutics Inc.
	Protocol Number: PLN-74809-IPF-202
STATISTICAL ANALYSIS PLAN. PHASE 2-3-4	

6.8 Prior and Concomitant Medications

Prior medications are defined as any medications taken prior to first dose of study drug but stopping before the date of first dose of study drug. Concomitant medications are defined as medications taken on or after the date of first dose of study drug.

Prior and concomitant medications will be presented by ATC Level 4 classification and Preferred Name for each treatment group in the Safety Population. All reported medications will be listed.

6.9 Exposure to Study Drug

Duration of exposure (in days) will be summarized by treatment group for the Safety Population. All exposure data, including changes in dosing recorded, will be listed.

6.10 Study Drug Compliance

Compliance (%) will be calculated for each participant and summarized by treatment group and overall. All compliance and study drug accountability data will be listed.

6.11 Efficacy Analyses

Efficacy analyses will be presented by randomized treatment for the Efficacy Intent-to-Treat (ITT) Population (unless otherwise specified). [REDACTED]

[REDACTED]

[REDACTED]

[REDACTED]

6.11.1 Spirometry

All spirometry parameters will be summarized using descriptive statistics by treatment group and visit for the [REDACTED] Population. Actual values, the changes from baseline and the percent changes from baseline will be presented for all scheduled visits along with 95% confidence intervals (CI) for the mean changes and mean percent changes from baseline.

The number and percent of participants showing an absolute decline in FVC (% Predicted) of $\geq 5\%$ and $\geq 10\%$ over the first 12 weeks will also be provided for each treatment group.

QMD [REDACTED]	[REDACTED]
Confidentiality Statement	
This document is the property of [REDACTED] and may not be duplicated, copied, altered or removed from company without prior approval from [REDACTED] or in compliance with [REDACTED].	

[REDACTED]

Controlled Quality Management Document		
	Sponsor:	Pliant Therapeutics Inc.
	Protocol Number:	PLN-74809-IPF-202
STATISTICAL ANALYSIS PLAN. PHASE 2-3-4		

The number and percent of participants showing a relative decline in FVC (% Predicted) of $\geq 5\%$ and $\geq 10\%$ over the first 12 weeks will also be provided for each treatment group.

A categorical summary of participants by FVC change relative to baseline (increase/ decrease) will be provided for Part D participants at Weeks 12 and 24.

A mixed model for repeated measures (MMRM) will also be utilized to analyze the change from baseline to each post-baseline visit in FVC (mL).

The MMRM model will [REDACTED]
[REDACTED]
[REDACTED]
[REDACTED]
[REDACTED]
[REDACTED]
[REDACTED]

The LS means, corresponding SEs, and 95% CI for each treatment group at each visit will be obtained from the model. An estimate for the LS mean difference (PLN-74809 vs. placebo), corresponding SE, 95% CI, and p-value for each dose group at each visit will also be presented.

Separate MMRM analyses [REDACTED]
[REDACTED]

[REDACTED] will be provided showing all available data (scheduled and unscheduled) for each individual participant over the study for the parameters listed below. One panel will be displayed per treatment group.

Plots will also be provided showing mean (\pm SD) for all treatment groups at each scheduled visit for all parameters. Each treatment group will be identified using different plot symbols. Plots will be shown for actual values, change from baseline and percent change from baseline. Baseline will be set to zero for change from baseline plots.

Spirometry parameters to be summarized by treatment group and visit include:

- FVC (mL) Actual
- % FVC Predicted
- [REDACTED]
- [REDACTED]

Confidentiality Statement	
This document is the property of [REDACTED] and may not be duplicated, copied, altered or removed from company without prior approval from [REDACTED] or in compliance with [REDACTED].	

Controlled Quality Management Document		
	Sponsor:	Pliant Therapeutics Inc.
	Protocol Number:	PLN-74809-IPF-202
STATISTICAL ANALYSIS PLAN. PHASE 2-3-4		

█ [REDACTED]

█ [REDACTED]

All spirometry data will be listed.

Sensitivity Analyses:

The MMRM will be repeated in the █ [REDACTED] █ [REDACTED] as sensitivity analyses. In addition, a sensitivity analysis will be conducted using the █ [REDACTED] █ [REDACTED]

A trimmed mean analysis trimming the participants █ [REDACTED] █ [REDACTED] will also be conducted for Part D participants.

In addition, FVC will be summarized using descriptive statistics by the following treatment groups at baseline and Week 12 for the Efficacy Intent-to-Treat Population:

- █ [REDACTED] █ [REDACTED]
- █ [REDACTED] █ [REDACTED]
- █ [REDACTED] █ [REDACTED]

Actual values, the changes from baseline and the percent changes from baseline will be presented along with 95% confidence intervals (CI) for the mean changes and mean percent change from baseline.

The two comparisons below will be performed via the MMRM on (a) FVC change from baseline at each visit, and (b) FVC percent change from baseline at each visit. Additionally, █ [REDACTED] █ [REDACTED] will test (a) FVC Week 12 change from baseline endpoint, and (b) FVC week 12 percent change from baseline :

- █ [REDACTED] █ [REDACTED]
- █ [REDACTED] █ [REDACTED]

As a further exploratory analysis, █ [REDACTED] will be utilized to analyze the change from baseline to Week 12 in FVC between subjects in each of the treatment group selections above, as well as in Part D alone (not pooled).

█ [REDACTED]	█ [REDACTED]
█ [REDACTED]	
█ [REDACTED] █ [REDACTED] █ [REDACTED] █ [REDACTED]	
█ [REDACTED]	█ [REDACTED]

Controlled Quality Management Document		
	Sponsor:	Pliant Therapeutics Inc.
	Protocol Number:	PLN-74809-IPF-202
STATISTICAL ANALYSIS PLAN. PHASE 2-3-4		

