7.14 Missed Assessments

Missed assessments will reported as such and will not be imputed.

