6.1.6 Efficacy Intent-to-Treat Population

The Efficacy Intent-to-Treat (ITT) Population includes all randomized participants.

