6.2.4 Early Termination Assessments

Early termination assessments will not be summarized. Early termination assessments will appear in the listings as recorded.

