6.2.8 Unscheduled Visits

Only scheduled post-baseline values will be tabulated. Post-baseline repeat / unscheduled assessments will not be summarized but will be listed in the relevant appendices to the CSR.

Controlled Quality Management Document		
	Sponsor:	Pliant Therapeutics Inc.
	Protocol Number:	PLN-74809-IPF-202
STATISTICAL ANALYSIS PLAN. PHASE 2-3-4		

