6.3.4 Summary Statistics

Continuous variables will be summarized by the number of non-missing observations, mean, median, standard deviation, and minimum and maximum.

Confidentiality Statement	
This document is the property of ██████████ and may not be duplicated, copied, altered or removed from company without prior approval from ██████████ or in compliance with ██████████.	

Controlled Quality Management Document		
	Sponsor:	Pliant Therapeutics Inc.
	Protocol Number:	PLN-74809-IPF-202
STATISTICAL ANALYSIS PLAN. PHASE 2-3-4		

Categorical variables will be summarized by presenting the frequency and percent. Percentages will be based on the number of non-missing observations or the participant population unless otherwise specified. For each variable, all categories will be shown. Zero frequencies (but not the percent) within a category will be presented.

Incidences of adverse events, medical history and concomitant medications will be reported at the participant level. Participants can only be counted once within each PT and SOC under the highest severity and most related. Percentages will be calculated using the number of participants in the treatment group for the Safety Population.

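### As far as the visible SAP shows, the FVC decline rates omit early-termination spirometry and do not say how participants lost before Week 12 are counted

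*SAP*

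**What the plan says.** SAP 6.11.1 (Spirometry) plans "The number and percent of participants showing an absolute decline in FVC (% Predicted) of" at least 5% and at least 10%, and the same for relative decline. The window is given only as "over the first 12 weeks will also be provided for each treatment group". No rule for death, dropout or a missing Week 12 value is attached in the visible text.

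Four general rules then apply:

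- **Early termination (SAP 6.2.4):** "Early termination assessments will not be summarized"; the values are listed only.
- **Unscheduled and repeat values (SAP 6.2.8):** "Only scheduled post-baseline values will be tabulated".
- **Missing data (Protocol 7.14):** "Missed assessments will reported as such and will not be imputed".
- **Denominator (SAP 6.3.4):** "Percentages will be based on the number of non-missing observations or the participant population unless otherwise specified".

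SAP 6.3.4 does settle the denominator for adverse events (the Safety Population in each group). Nothing visible does so for FVC decline. The default efficacy population in SAP 6.11 is ITT, and SAP 6.1.6 says "The Efficacy Intent-to-Treat (ITT) Population includes all randomized participants", but that default allows exceptions and the lines after it are redacted.

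**The concern.** Read together, these rules discard relevant measured data and leave the treatment of losses open. Protocol Section 11 sends a participant who withdraws or discontinues study drug to early-termination assessments. If FVC has fallen by then, SAP 6.2.4 keeps that value out of the table.

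IPF is progressive and fatal (Protocol Section 1), so some losses inside 12 weeks may be participants who were getting worse. The rates are shown by dose beside placebo, and Protocol 3.2 says the results will feed into dose choice for later IPF trials. If one group loses more worsening participants than another, its decline rate could look better than it was.

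**Working it through.** **1. Group sizes, reproduced from the plan.** Part B: 28 × 3/4 = 21 active, 7 placebo. Part C: 56 × 3/8 = 21 at each of two doses, 56 × 2/8 = 14 placebo. Part D: 28 × 3/4 = 21 active, 7 placebo. Active 4 × 21 = 84; placebo 7 + 14 + 7 = 28; total 112. This matches Protocol 3.1 and 12.2. SAP 6.3.6 displays each dose, all active combined, and a single placebo column.

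**2. What the visible rules do with each kind of loss.**

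| Participant | Window means at Week 12 | Window means any scheduled visit to Week 12 |
|---|---|---|
| Decline at an earlier scheduled visit, then leaves | Left out or non-decliner | Counted as decline |
| Decline first measured at early termination within 12 weeks | Not counted | Not counted |
| Dies or leaves with no tabulated decline | Left out or non-decliner | Left out or non-decliner |

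The second row is the same under both readings. It assumes that spirometry is done at the early-termination visit; the relevant row labels in the Protocol Appendix 1 schedule are redacted.

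**3. Error in the rate.** Let n be randomized, m lost with no tabulated qualifying value, p the decline proportion in those observed and q that in those lost.

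- All-participant rate = [(n − m)p + mq]/n
- Losses left out: reported rate p, error = −(m/n)(q − p)
- Losses as non-decliners: reported rate (n − m)p/n, error = −(m/n)q

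The first error is zero when q = p and changes sign when q < p. The second is negative whenever q > 0.

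**4. Size.** The documents give no dropout or decline rate, so p = 20% and the ranges for m and q are assumptions; n = 21 is the plan's. Results are expected values.

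| q | Error if left out, m = 1 to 4 | Error if non-decliner, m = 1 to 4 |
|---|---|---|
| 20% | 0 | −1.0 to −3.8 points |
| 50% | −1.4 to −5.7 points | −2.4 to −9.5 points |
| 100% | −3.8 to −15.2 points | −4.8 to −19.0 points |

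For one lost true decliner: (20 × 0.2 + 1)/21 = 23.8%, against 20.0% (left out) or 4/21 = 19.0% (non-decliner).

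**5. Denominator alone, same data.** Assume 21 randomized, 3 lost, 4 observed decliners: 4/18 = 22.2% or 4/21 = 19.0%, a gap of 3.2 points. Counting the 3 losses as decline gives 7/21 = 33.3%.

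**6. Two-arm illustration (assumed counts).** Active 21 with 6 true decliners, 3 of them lost; pooled placebo 28 with 8 decliners, none lost. True rates are 6/21 = 8/28 = 28.6%. The table would show active at 3/18 = 16.7% or 3/21 = 14.3% against 28.6%, an apparent benefit of 11.9 or 14.3 points where none exists.

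**7. One placebo participant.** In the pooled placebo column, 1/28 = 3.6 points.

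**The case against.** The strongest reply is redaction. Text is blacked out in SAP 6.2.5 (Spirometry Assessments), after the ITT sentence in SAP 6.11, and where SAP 6.11.1 names the population for the spirometry summaries. Any of these could hold a rule for losses. This stands, and the point is limited to what can be read.

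Second, the window may mean any visit up to Week 12. The SAP names specific visits elsewhere, for example for the cough responder count. On that reading a participant who declined at a scheduled visit and then left is counted. This stands, but it does not rescue a decline first seen at early termination.

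Third, a reader might infer that the rates must favour whichever arm loses more participants. The documents do not support that. Leaving losses out biases the rate only if those lost decline at a different rate from those observed, and Protocol Section 11 lists reasons for leaving that need not reflect worsening IPF. The population is mild to moderate, and Protocol 3.1 asks those who stop drug for safety reasons to stay for all remaining assessments. Section 11 also sends those who discontinue drug to early-termination assessments, so the two passages need to be reconciled.

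Fourth, a reader might take the 7 planned Part D placebo participants and conclude that one person moves the rate by 1/7 = 14.3 points. That would apply only to a Part D-only placebo column. The decline rates are planned by treatment group, and SAP 6.3.6 shows one pooled placebo column.

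Finally, losses are visible elsewhere: SAP 6.4 tabulates early termination with reasons, adverse events leading to death or termination are reported, all spirometry is listed, and FVC change is also analysed by MMRM. A careful reader could piece the losses together. The decline percentages themselves would still not reflect them.

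**Conclusion.** The point holds for the visible SAP. An early-termination FVC decline within 12 weeks is excluded by a stated rule, and a participant lost with no tabulated decline is either dropped or counted as a non-decliner, with neither option chosen. Counting losses as non-decliners understates the rate whenever any of them declined; leaving them out does so only if they decline more often than those observed.

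With 20% decline assumed among those observed in an arm of 21, the cost is about 3.8 or 4.8 points per lost true decliner. No actual bias is shown, since that depends on dropout and decline rates the documents do not give. The conclusion also assumes that no redacted passage supplies a rule and that spirometry is part of the early-termination visit. Protocol 12.1 states that no hypotheses are tested and the measure is exploratory and descriptive, so no sample size or error rate is affected.

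**What to change.** Unless the redacted text already does so:

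1. For these tables only, make an exception to SAP 6.2.4 so that early-termination FVC obtained within the 12-week window counts.
2. Use the ITT denominator for both thresholds, absolute and relative.
3. State whether the window means at Week 12 or at any visit up to Week 12.
4. Show the number missing by arm and reason.
5. Add a supplementary version in which death, or discontinuation without a Week 12 FVC, counts as decline, beside the observed-data version.

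The cost is SAP wording and one extra set of rows per table; no new data are needed. The downside is that the supplementary version may count some dropouts unrelated to disease as decline, which is why both versions should be reported.

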6.11.1 Patient-Reported Cough

Descriptive statistics for the patient-reported VAS for cough and change from baseline will be summarized by treatment group and visit for the Safety Population. The number and percent of participants with VAS ≥ 40 at Baseline and reduction in VAS of ≥ 30 at Week 12 (as described in [REDACTED]³) will also be provided by treatment group. Mean (\pm SD) change from baseline will also be presented graphically by treatment group. All collected VAS data will be listed.

6.11.2 Quantitative Lung Fibrosis

Collection data for HRCT scans performed will be listed. Analysis of QLF (assessed by HRCT) will be described in a separate analysis plan.

6.12 Pharmacokinetic Analyses

6.12.1 Concentration-Time Data

In study Parts B and C, plasma samples will be taken [REDACTED] relative to PLN-74809 dosing on [REDACTED]. In study Part D, plasma samples will be taken [REDACTED] relative to PLN-74809 dosing on [REDACTED].

Concentration data will be obtained for PLN-74809 [REDACTED].

[REDACTED] PLN-74809 concentration [REDACTED] will be calculated as follows:

- [REDACTED]
- [REDACTED]

PLN-74809 concentration data ([REDACTED]) will be summarized by dose level and visit at each scheduled sample time (nominal time) using descriptive statistics: number of non-missing observations (n), arithmetic mean (mean), standard deviation (SD), median, minimum (min), maximum (max), and coefficient of variation (CV%). Scatter plots will also be provided showing mean (SD). Similarly, [REDACTED] will be

QM [REDACTED]	[REDACTED]
Confidentiality Statement	
This document is the property of [REDACTED] and may not be duplicated, copied, altered or removed from company without prior approval from [REDACTED] or in compliance with [REDACTED]	

Controlled Quality Management Document		
	Sponsor:	Pliant Therapeutics Inc.
	Protocol Number:	PLN-74809-IPF-202
STATISTICAL ANALYSIS PLAN. PHASE 2-3-4		

summarized. Concentrations that are below the limit of quantification (BLQ) will be set to zero for summary statistics. BLQ concentrations will be retained as BLQ in listings. The data will be reported to 3 significant figures.

Individual PLN-74809 [REDACTED] [REDACTED]), nintedanib, and pirfenidone concentration data will be provided in listings. Data may be pooled with data from other studies for population PK and reported outside of the clinical study report.

6.12.2 PK Parameters

Not applicable.

6.13 Pharmacodynamic Analyses

Biomarker results obtained from urine, plasma or serum samples will be summarized using descriptive statistics by treatment group and visit for each parameter. Actual biomarker concentration at each visit, the change from baseline and percentage change from baseline will be presented. The result adjusted for dilution factor will be used in summaries and listings. Samples hemolyzed, received ambient or with a note indicating improper storage will be excluded from summaries and listed only. If a sample has been excluded, then the change from baseline for that sample will also not be calculated.

Actual biomarker concentrations will be presented as a line plot showing the mean (\pm SD) concentration at each visit by treatment group for each parameter.

For biomarkers with at least 2 post-baseline scheduled assessments, absolute change from baseline and percentage change from baseline will be presented as a line plot showing baseline (0) and the mean (\pm SD) concentration at each post-dose visit by treatment group for each parameter.

For biomarkers with only one post-dose scheduled assessment, absolute change from baseline and percentage change from baseline will be presented by box and whisker plot for each treatment group.

Change from baseline to each visit will also be analyzed for all biomarkers using an MMRM [REDACTED] [REDACTED] LS means (\pm SE) for each treatment group and estimate for treatment difference compared to placebo, with corresponding SE, 95% CI and p-value will be provided .

QMD [REDACTED]	[REDACTED]
Confidentiality Statement	
This document is the property of [REDACTED] and may not be duplicated, copied, altered or removed from company without prior approval from [REDACTED] or in compliance with [REDACTED].	

Controlled Quality Management Document		
	Sponsor:	Pliant Therapeutics Inc.
	Protocol Number:	PLN-74809-IPF-202
STATISTICAL ANALYSIS PLAN. PHASE 2-3-4		

